## **The study**

This study has addressed topics of related to healthy lifestyle, in addition to nutrition and exercise. Topics of the Health-Promoting Lifestyle Education Program (**HPLEP**) were self-management of blood glucose, nutrition, physical activity, coping with stress, sleeping, smoking, self-care and breastfeeding. Within the scope of the **HPLEP**, one-to-one applied education and counseling were provided to the women using written and visual materials.

## **Aim**

The aim of the study was to examine the effects of the **HPLEP** on maternal and neonatal health.

Hypotheses of this study;

H1: The **HPLEP** is effective for women with GDM in their adoption of a healthy lifestyle.

H2: The **HPLEP** is effective in reducing the symptoms of depression in women with GDM.

H3: The **HPLEP** is effective in improving the quality of life of women with GDM.

H4: The **HPLEP** is effective in reducing postpartum neonatal complications.

## **Desing**

The study was designed and conducted as a two group quasi-experimental study. Intervention group (n=46) and control group (n=42) were administered the data collecting tools in the first assessment. After first assessment, the intervention group were included in the educational program. Data collecting tools were re-administered four weeks after to the intervention group only. Than data collecting tools were re-administered to the both groups in the postpartum 6th week.

## **Sample**

This study was conducted in the perinatology clinic of the Istanbul Zeynep Kamil Hospital, Turkey in 2015. The records show that 350 women with GDM were referred to the perinatology clinic in that period. The sample size was calculated using Power and Sample Size Program, with 80% power and a 0.05 margin of error, and it was

determined that both the intervention and the control group should include at least 30 women with GDM. It was considered appropriate that 50 women with GDM be included in each group.

The inclusion criteria for participation in the study included a gestational period of 24 to 34 weeks, a diagnosis of GDM, an age of 18 years or older, and voluntary consent to participate in the study, while the exclusion criteria included the presence of a psychiatric disease, multiple pregnancy, the risk of preterm labor, placenta previa or premature rupture of the membranes, and failure to obtain voluntary consent to participate in the study.

### **Data collection**

Data were collected by the first author (both control and intervention group). All data were collected with questionnaires conducted through face-to-face structured interviews with the data collector.

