#### *Primary outcomes:*

- Primary outcome of women with GDM was their healthy lifestyle behaviours measured on the Health-Promoting Lifestyle Profile II (HPLP-II). This scale, developed by Walker et al. (1987) on the basis of Pender's health promotion model, measures the health-promoting behaviours associated with a health-promoting lifestyle. The scale was revised in 1996 and designated as HPLP-II (Walker et al. 1996). Bahar et al. (2008) tested the scale's validity and reliability in Turkish. The Cronbach's alpha internal consistency coefficient of the scale was found to be 0.92. Higher scores on the scale indicate a higher performance level of the determined health-promoting behaviours. The scale consists of 52 items under the six subscales of spiritual growth, nutrition, physical activity, health responsibility, interpersonal relations and stress management. The lowest and highest possible scores on the scale are 52 and 208, respectively.

- Center for Epidemiologic Studies Depression Scale (CES-D Scale) was used to assess symptoms of depression in women. This short scale, developed by Radloff (1977) to measure depressive symptoms, can be administered to both the general population and specially selected groups. The CES-D consists of 20 items, each item scored between 0 and 3. The total score ranges between 0 and 60, and a score of 16 and higher suggests the risk of depression, while lower scores on the CES-D Scale indicate decreased risks for depression. Yilmaz (2010) tested the scale's validity and reliability in Turkish. The Cronbach's alpha value was found to be 0.85 for the entire scale.
- Quality of life of the women was measured using the Short Form 36 Health Survey (SF-36). This scale, developed by Ware in 1987, is globally referred to as SF-36, as this acronym has been commonly used in all studies since the development of the scale. SF-36 is a self-assessment scale, consisting of 36 questions under eight subscales: physical functioning, physical role limitation, social functioning, mental health, energy-vitality, bodily pain, general health perceptions and emotional role limitation (Ware & Sherbourne 1992). Pınar (1995) tested the scale's validity and reliability in Turkish. The Cronbach's alpha internal consistency value was found to be 0.91.

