#### *Secondary outcomes*

- Postpartum diabetes control of women with GDM was assessed through the postpartum 6th week information form that developed by the researchers on the basis of the literature.
- Postpartum characteristics of neonates were assessed through the neonate's information form that developed by the researchers on the basis of the literature.

The flowchart of this study is shown in Figure 1. The patients followed up in the perinatology clinic were assigned to groups through randomization (drawing lots by the clinic nurse). Data collector checked patients in the perinatology clinic daily. If there were more than one patient who met the inclusion criteria, it was determined which group to take with the lottery method. When there was only one woman with GDM in the clinic, it was determined which group to take with the lot but the next patient was taken directly to the opposite group. When two patients were in the same room, they were taken into the same group in order not to have any ethical problems. The women in the both group were administered the introductory information form, the HPLP-II, the CES-D and the SF-36 in the first assessment.

The education program and also usual care applied to the intervention group. The education program consisted of three 45-min sessions, which included a face-to-face lecture with the dissemination and presentation of written and visual materials. Also each participant in the intervention group was given the *Health-Promoting Lifestyle Booklet* and the *Diary of a Woman with GDM* card. The booklet features all of the health-promoting practices (self-monitoring of blood glucose, nutrition, physical activity, stress, sleeping, smoking, self-care and breastfeeding). The *Diary of a Woman with GDM* card features the daily program that women should follow (the hours for main meals and snacks, insulin hours, etc.). The education and counseling were maintained through follow-up via phone for intervention group.

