The women in the control group which receiving only usual care were followed according to the institution's routine diabetes follow-up protocol (monitoring blood glucose levels as frequently as indicated by the doctor, and patients are referred to dietitian and to diabetes nurse). To assess the effectiveness of the educational program, the HPLP-II, CES-D and SF-36 were re-administered to the intervention group four weeks after the first assessment (second assessment). The HPLP-II, CES-D and SF-36 were re-administered to the both groups in the postpartum 6th week (third assessment).

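### The three self-report primary scales are asked face to face by one author who can be inferred to know the group, so a reporting shift in the educated women could pass for a program effect, most plausibly on HPLP-II

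*Combined protocol and SAP*

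**What the plan says.** All references are to the combined protocol and SAP.

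- **Who collects, and how.** The Data collection section states: "Data were collected by the first author (both control and intervention group". It continues: "All data were collected with questionnaires conducted through face-to-face structured interviews with the data collector".
- **What is collected.** The Primary outcomes section lists HPLP-II, CES-D and SF-36, which correspond to H1, H2 and H3 in the Aim section. All three are self-reports. The plan itself describes one of them this way: "SF-36 is a self-assessment scale, consisting of 36 questions under eight subscales".
- **When.** Both groups have a first assessment, before the education. The Desing section then says: "Data collecting tools were re-administered four weeks after to the intervention group only". Both groups are assessed again at six weeks postpartum (third assessment).
- **What differs between groups.** The procedures under Secondary outcomes give intervention women three 45-minute sessions, a booklet of health-promoting practices, a diary card and telephone follow-up, on top of usual care. Controls have usual care only, which includes referral to a dietitian and a diabetes nurse.
- **How it is analysed.** The Data analysis section compares the groups by Mann-Whitney test at the first and third assessments. The three assessments of the intervention group are compared with one another by Wilcoxon signed-rank test.

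The plan mentions no blinding of the collector, no self-completion, no independent interviewer and no masked scoring. The Validity and reliability section covers allocation and Cronbach's alpha only.

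**The concern.** Answers to subjective items can depend on who asks and on what the respondent thinks the asker hopes to hear. Here the asker is an author of the study. One group has been taught, shortly beforehand, that the behaviours in question are the right ones. HPLP-II has subscales on nutrition, physical activity and stress management, which are also topics of the program. A woman in the intervention group may therefore report more of these behaviours than she practises, and to a greater degree than a control would.

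The third-assessment comparison is the only controlled test of the three scales after the education. The Wilcoxon comparisons have no control group and cannot separate reporting from real change. If part of the between-group difference comes from reporting, a positive finding, on H1 above all, cannot be attributed to the program alone.

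**Working it through.** The plan gives no figure on this point to reproduce. Its minimum of 30 women per group is stated without an effect size and does not bear on the question. The check has three parts.

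**1. Does the collector know the group?** The documents do not say so; it has to be inferred.

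- One person collects all data in both groups (Data collection).
- The four-week assessment goes to intervention women only (Desing, and again in the procedures).
- So by the third assessment that person has already re-interviewed the intervention women and none of the controls.

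This inference is firm. Two other passages lend it weaker support. The procedures say "Data collector checked patients in the perinatology clinic daily", and that after a lone patient's lot "the next patient was taken directly to the opposite group", which makes some assignments predictable. But the clinic nurse drew the lots, and these passages do not show that the collector saw the result.

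**2. Can baseline scores remove the shift?** Let δ be the true effect of the program and b the difference between groups in reporting shift, both in SD units. The first assessment precedes the education, so b is absent there. The expected between-group difference is then:

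- at the third assessment: δ + b
- in change from first to third assessment: (δ + b) − 0 = δ + b

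Either way only the sum can be estimated. Cronbach's alpha does not help, because it measures agreement among items and cannot detect a shift common to all of them.

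**3. How sensitive is the test to b?** Inputs: 46 and 42 women (Desing), taken as all assessed at the third assessment; normally distributed scores; two-sided 0.05; δ = 0. The values of b are assumptions.

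- SE = √(1/46 + 1/42) = √(0.02174 + 0.02381) = 0.2134 SD
- Smallest observed difference that reaches significance: 1.96 × 0.2134 = 0.42 SD
- Chance of a significant result favouring the program: 1 − Φ(1.96 − b/SE)
  - b = 0.2: 1 − Φ(1.96 − 0.937) = 1 − Φ(1.023) = 15.3%
  - b = 0.3: 1 − Φ(1.96 − 1.406) = 1 − Φ(0.554) = 29.0%

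The planned test is Mann-Whitney, so it was also simulated directly. The first simulation used 8,000 runs per setting; the second is an independent repeat.

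| Assumed shift b (SD) | Mann-Whitney, simulation | Mann-Whitney, repeat | Normal approximation, favouring the program |
|---|---|---|---|
| 0 | 4.6% | 4.9% | 2.5% |
| 0.2 | 13.8% | 14.9% | 15.3% |
| 0.3 | 26.5% | 26.9% | 29.0% |
| 0.5 | 61.8% | 61.7% | 64.9% |

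The simulated columns count significant results in either direction, so their reference at b = 0 is 5%. The last column counts one direction only, so its reference is 2.5%. The simulations agree to within about one percentage point. With fewer women at the third assessment, the SE would be larger and the percentages for the same non-zero b smaller.

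**The case against.** The strongest reply is that the documents show a missing safeguard, not a bias. The percentages are a power curve that would apply to any two-group study of this size with a subjective outcome. They show how sensitive the test is, not how likely a shift is. That stands, and the figures should be read only in that way.

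A reader might go further than the documents allow in four ways:

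- **That all three scales are biased in favour of the program.** The mechanism fits HPLP-II best. It is weaker for CES-D and for SF-36 items such as bodily pain and physical functioning. Coping with stress is taught, so some spill-over is plausible, but familiarity with the interviewer could also lead women to disclose more depressive symptoms.
- **That controls feel no pressure.** They answer the same questions, face to face, to the same author, and usual care refers them to a dietitian and a diabetes nurse. Only the difference in pressure between groups biases the comparison.
- **That the collector is documented as unblinded.** This is an inference, and it rests on the intervention-only assessment.
- **That women are answering their own teacher.** The documents do not say who gave the sessions or made the calls.

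The chosen method also has a merit: one collector with a structured interview keeps wording uniform and removes variation between interviewers. That does not address knowledge of group.

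**Conclusion.** The concern holds as an avoidable weakness of outcome assessment. Self-report primary scales are taken face to face by a single author, without blinding or self-completion, and the design itself reveals the group to that author before the only controlled post-education comparison. The result could favour the program, most plausibly on H1 and with less certainty on H2 and H3.

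The size of any shift is unknown, and nothing in the documents shows that one occurred. Under the stated assumptions (no true effect, normal scores, 46 and 42 women assessed), a differential shift of 0.2 SD, about half the difference needed for significance, raises the rejection rate from 5% to about 14–15%. A shift of 0.3 SD raises it to about 27%. A significant third-assessment result is therefore not, by itself, evidence that behaviour rather than reporting changed.

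**What to change.** **For data already collected.** The document describes the study as conducted, so this part applies directly. State in the conclusion that H1 to H3 rest on self-reports taken face to face by an investigator who was not blinded. Word the H1 finding as a difference in reported behaviour. The cost is a sentence or two.

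**For the plan, or any repeat of it.** In Data collection and in the assessment procedures under Secondary outcomes:

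- Have women in both groups complete HPLP-II, CES-D and SF-36 themselves, on paper and in private.
- Have forms returned in a sealed envelope marked with a study number only, and score them without group labels.
- Limit reading aloud to women who need it, and record the mode for every form.
- Report the third-assessment comparison with and without interviewer-read forms. The second version leaves out women with limited literacy, so treat it as a sensitivity analysis.

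This uses the same forms, visits and staff. The price is some more missing items and help for women with limited literacy; the documents do not report literacy, so the number needing help is unknown. The change removes the interviewer component only. Women still know whether they had the education, so expectancy bias remains and should be acknowledged.

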#### *Primary outcomes:*

- Primary outcome of women with GDM was their healthy lifestyle behaviours measured on the Health-Promoting Lifestyle Profile II (HPLP-II). This scale, developed by Walker et al. (1987) on the basis of Pender's health promotion model, measures the health-promoting behaviours associated with a health-promoting lifestyle. The scale was revised in 1996 and designated as HPLP-II (Walker et al. 1996). Bahar et al. (2008) tested the scale's validity and reliability in Turkish. The Cronbach's alpha internal consistency coefficient of the scale was found to be 0.92. Higher scores on the scale indicate a higher performance level of the determined health-promoting behaviours. The scale consists of 52 items under the six subscales of spiritual growth, nutrition, physical activity, health responsibility, interpersonal relations and stress management. The lowest and highest possible scores on the scale are 52 and 208, respectively.

- Center for Epidemiologic Studies Depression Scale (CES-D Scale) was used to assess symptoms of depression in women. This short scale, developed by Radloff (1977) to measure depressive symptoms, can be administered to both the general population and specially selected groups. The CES-D consists of 20 items, each item scored between 0 and 3. The total score ranges between 0 and 60, and a score of 16 and higher suggests the risk of depression, while lower scores on the CES-D Scale indicate decreased risks for depression. Yilmaz (2010) tested the scale's validity and reliability in Turkish. The Cronbach's alpha value was found to be 0.85 for the entire scale.
- Quality of life of the women was measured using the Short Form 36 Health Survey (SF-36). This scale, developed by Ware in 1987, is globally referred to as SF-36, as this acronym has been commonly used in all studies since the development of the scale. SF-36 is a self-assessment scale, consisting of 36 questions under eight subscales: physical functioning, physical role limitation, social functioning, mental health, energy-vitality, bodily pain, general health perceptions and emotional role limitation (Ware & Sherbourne 1992). Pınar (1995) tested the scale's validity and reliability in Turkish. The Cronbach's alpha internal consistency value was found to be 0.91.
- Women's level of knowledge about GDM was measured using pre-test and post-test question form. This form, developed by the researcher in accordance with the literature, includes questions about GDM and healthy lifestyle.

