### **Validity and reliability**

Women with GDM in the intervention and control group were divided into groups by randomization method. Women with GDM who were followed up in the perinatology clinic were divided into groups by means of a lottery method. In the clinic, women in

the same room were not taken to different groups to avoid problems among GDM women.

In this study reliability of the instruments was measured with Cronbach's alpha. The Cronbach's alpha value of the HPLP II was 0.90; the CES-D was 0.85 and the SF-36 was 0.85.

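### H3 names no SF-36 test score among eight subscales, and H1 to H3 could be claimed from intervention-group changes that have no control

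*Combined protocol and SAP*

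**What the plan says.** - **Hypothesis.** Under Aim, H3 states that the program "is effective in improving the quality of life of women with GDM". It gives no score and no time point.
- **Instrument.** Under Primary outcomes, "SF-36 is a self-assessment scale, consisting of 36 questions under eight subscales". No total, component summary or leading subscale follows. The same section gives an overall range of 52 to 208 for HPLP-II and a total of 0 to 60 for CES-D.
- **Reliability.** One alpha is quoted for the whole SF-36: 0.91 from the Turkish validation, and in this study "the CES-D was 0.85 and the SF-36 was 0.85".
- **Other listed outcomes.** Four measures stand under Primary outcomes. The first is introduced in the singular: "Primary outcome of women with GDM was their healthy lifestyle behaviours measured on the Health-Promoting Lifestyle Profile II (HPLP-II"). The fourth is knowledge: "level of knowledge about GDM was measured using pre-test and post-test question form". No hypothesis in Aim concerns knowledge.
- **Assessments.** The Design section reports "Intervention group (n=46) and control group (n=42) were administered the data collecting tools in the first assessment". The procedures text under Secondary outcomes then says "To assess the effectiveness of the educational program, the HPLP-II, CES-D and SF-36 were re-administered to the intervention group" four weeks later, and that the scales were "re-administered to the both groups in the postpartum 6th week (third assessment").
- **Analysis.** The Data analysis section uses Mann-Whitney between groups at the first and third assessments, and Wilcoxon within the intervention group for the three assessments and for the pre-post test. It names no score for any scale and no multiplicity rule. It places the third assessment at the sixth postpartum month, where the Design and procedures texts say week.

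**The concern.** Two routes to a positive claim are left open.

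First, eight SF-36 comparisons could be run for H3. With no score named and no adjustment, nothing in the plan prevents H3 from being declared on whichever subscale is significant.

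Second, the plan itself assigns the judgement of effectiveness to an assessment that the control group did not have. Change within the intervention group from mid-pregnancy to four weeks later, or to the postpartum visit, mixes any effect of the program with the course of pregnancy and recovery, usual care and repeated questioning. A significant Wilcoxon test does not separate these, yet it could be offered in support of H1, H2 or H3. The knowledge comparison has the same limitation.

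The first assessment precedes the program, so the third is the only between-group comparison that can show an effect. Its timing is stated in two ways.

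**Working it through.** **The plan's own figure.** The Sample section gives at least 30 women per group for 80% power at 0.05. This cannot be reproduced, because no outcome, effect or SD is given. Solving backwards for a two-sided test, d = √[2(1.960 + 0.842)²/30] = 0.72. It does not show which score the study was sized on and is not used below.

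**1. How far each score is defined**

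| Hypothesis | Scale | Subscales listed | Overall score range | Score named in Data analysis |
|---|---|---|---|---|
| H1 | HPLP-II | 6 | 52-208 | none |
| H2 | CES-D | none | 0-60 | none |
| H3 | SF-36 | 8 | none | none |

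**2. Error rate for H3.** Assumptions, none stated in the documents: each of the eight subscales is compared between groups at two-sided 0.05, one significant result is enough, and all pairs of subscales share one correlation ρ.

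At ρ = 0 the results are exact:
- any direction: 1 − 0.95⁸ = 33.7%
- favourable only: 1 − 0.975⁸ = 18.3%

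For ρ > 0, equicorrelated normal test statistics were simulated (400,000 draws):

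| ρ | Favourable, unadjusted | Any direction, unadjusted | Favourable, Holm | Any direction, Holm |
|---|---|---|---|---|
| 0 | 18.3% | 34% | 2.5% | 4.9% |
| 0.3 | 15% | 30% | 2.3% | 4.6% |
| 0.5 | 12.5% | 25% | 2.0% | 4.0% |
| 0.7 | 9.5% | 19% | 1.6% | 3.1% |

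With a single score the rates are 2.5% favourable and 5% in any direction.

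**3. Which correlation is plausible.** If the quoted alphas were computed over eight subscale scores (not stated), alpha = 8r/(1 + 7r), so r = alpha/(8 − 7·alpha). This gives 0.85/2.05 = 0.41 and 0.91/1.63 = 0.56. It is indicative only, but it makes ρ near 0.5 more representative than ρ = 0.

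**4. Power under Holm.** Assumptions: a true shift of 0.6 SD (no source in the documents), and all 46 and 42 women reaching the third assessment (follow-up numbers are not shown). Mann-Whitney efficiency is taken as 3/π.

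- Noncentrality: 0.6 × √[(46 × 42/88) × 3/π] = 2.75.
- One given subscale at 0.05: Φ(2.75 − 1.96) = 78%; noncentral t gives 77.5%.
- One given subscale at Holm's first step, 0.05/8 = 0.00625: Φ(2.75 − 2.73) = 51%; noncentral t gives 48%.
- With an assumed 10% loss (41/38), noncentral t gives 73% falling to 42%. With 20% loss (37/34), it gives 68% falling to 37%.
- Chance that at least one subscale passes at ρ = 0.5 with 46/42 (normal approximation): 51% if one subscale shifts, 67% if two, 80% if four, 89% if all eight.

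**5. Comparisons with and without a control**

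| Comparison | Groups | Test |
|---|---|---|
| First assessment | both | Mann-Whitney (baseline) |
| Second (four weeks) | intervention only | Wilcoxon |
| Third (postpartum) | both | Mann-Whitney |
| Change across the three assessments | intervention only | Wilcoxon |
| Pre-post test, probably the knowledge form | intervention only | Wilcoxon |

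Only the third row can support a claim that the program works.

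**The case against.** The strongest reply is that the documents nowhere say that one significant subscale is enough for H3. Reporting all eight as a profile fits the text equally well, and if one overall score was analysed the error rate is nominal. The single alpha for SF-36 may hint at such a score. This stands in part. What is shown is an unstated rule, and the percentages describe what that gap permits. But an alpha measures internal consistency and does not say which score is tested.

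A reader might infer that H3 has a 34% false-positive rate. The documents do not support that. It is the boundary case of zero correlation, it counts results in both directions, and it presumes a decision rule that the plan does not state.

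H3 is also not alone in lacking a named score, since the Data analysis section names none for HPLP-II or CES-D. That is fair, but their stated overall ranges point to a total; SF-36 has nothing comparable.

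A reader might further infer that the four listed primary outcomes must be ranked, with HPLP-II alone as primary. H1 to H3 are separate hypotheses. With one score per scale, the chance of any false difference over the three scales is about 11-14% at correlations from 0.7 to 0. Treating HPLP-II and CES-D at 0.05 with Holm inside SF-36 gives about 9-14%. Demoting listed outcomes after the fact is a matter of preference and gains little.

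Finally, between-group tests are planned, so a claim resting on uncontrolled change is a possibility and not a certainty. The month in the Data analysis section may be a slip, since the other mentions say week.

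**Conclusion.** The point holds in a limited form. The plan does not say which SF-36 result decides H3, and it treats an assessment without controls as evidence of effectiveness.

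Under the assumed any-subscale rule, a false favourable H3 has a probability of about 18% at correlation 0, 13% at 0.5 and 9-10% at 0.7, against 2.5%; in any direction the figures are 34%, 25% and 19%. These rest on equal correlations and two-sided 0.05 tests, neither of which the documents state. The inflation vanishes if one score is tested. The risk from uncontrolled comparisons is real but cannot be quantified from the documents.

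This should be corrected in analysis and reporting. It does not show that an inflated claim was made, and it gives no ground for re-ranking the listed primary outcomes.

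**What to change.** 1. Report all eight SF-36 subscales. Claim H3 only for those whose between-group comparison at the third assessment favours the intervention and passes Holm across the eight. If a record dated before the analysis names one SF-36 score, test that score at 0.05 instead.
2. Base H1 to H3 only on the between-group comparison at the third assessment. Report the within-intervention Wilcoxon results and the knowledge pre-post results descriptively.
3. Reconcile the timing of the third assessment between the Design and procedures texts (week) and the Data analysis section (month).
4. Disclose that these rules were set after the study was conducted.

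**Cost.** No new data are needed. The smallest SF-36 p-value must reach 0.00625. At the assumed 0.6 SD with 46/42 women, power for one given subscale falls from about 78% to 48-51%, and further with losses to follow-up. The loss is smaller if the program acts broadly: at correlation 0.5, at least one subscale passes with probability 67% if two shift, 80% if four and 89% if all eight. A single score shown to have been fixed before the analysis would avoid the penalty.
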